Participants will have weights measured in private rooms. Families will also learn the core components of the program in presentations by the research staff. The workshop will also include activities to keep the families engaged and a meal will be provided. If the participants attend the workshop, successfully logged in MyFitnessPal, and still want to participate, they will be randomized to a treatment group and scheduled for a baseline session.

Session 3- Baseline: \sim 1 Hour 30 Minutes; In Lab Session Participants will complete the following:

1- Have height and weight measured.

2- Complete surveys: Consideration of Future Consequences Scale (CFCS), Palatable Eating Motives Scale (PEMS), and Living to 75 assessment.

3- Complete the Delay Discounting Task

4- Complete EFT or CONTROL cue generation needed for thought training.

EFT Cues: A brief cue will be generated in which participants talk about a specific future positive event where they imagine themselves in vivid detail. To generate the cues, participants in the EFT group will be given standardized instructions asking them to think about and list specific events that they are looking forward to in the future (ex: parties, holidays, etc.). Participants will be instructed to generate the EFT cue by describing their events, including a detailed description of themselves at the specific event. After the cue is created, participants will rate this cue for valence, salience, arousal, and the frequency and vividness of episodic associations. Participants who do not rate the cue at least 3 out of 5 for vividness will be asked to generate a new cue using a different event. After the participant has created their cues, they will save their cue for later use in the intervention.

Control Cues: To control for the timing and attention of the EFT cue, participants in the CONTROL group will generate cues that include a specific nutrition statements, selecting cues that they feel will be of personal benefit. To generate the cues, participants in the CONTROL group will select from a list of nutrition statements that they feel will be personally useful in making healthy decisions. After the cue is created, participants will rate this cue for salience. After the participant has created their cues, the participant will save their cue for later use in the intervention.

5- Go through a technology tutorial: Participants will be learning to use 2 major technologies for this study including:

EFT or CONTROL Cue Retrieval: The experimenter will then train participants in both groups on how to retrieve cues from their cell phone or alternative WiFi device, to pay attention to and think about the cues, and how to adhere to the study's expectations for utilizing to the cues. Participants will be told to use their cues any time they need to, especially around eating episodes, using the prompt response website - Mobile Audio Management and Response Tracker (MAMRT) (Sze, Daniel, Kilanowski, Collins, Epstein, 2015).

At-home weighing: Participants will send their weights to the researchers from a wireless scale provided to them by the researchers. During this baseline session, participants will be given a tutorial on how to use the wireless scale and associated application to send their weekly weights.

Sessions 4-19-Intervention Sessions

The intervention sessions will be separated into 2 phases.

PHASE 1: Sessions 4-10; ~ 30 minutes; In Lab Sessions

Participants will have weight measured, do the thought training program, talk to staff about progress in the program, and receive money from the monetary incentives program. For the monetary incentives program, each participant can earn \$20 for meeting their weight loss goals (parent=1 pound, child= 1/2 pound) each week. If both the parent and child meet their weight loss goals, they will earn an additional \$5 a piece each week.

The monetary incentive is based on the lowest weight in the study. For example: Let's say the participant's starting weight at Session 3 is 250 and she has a weekly weight loss goal of 1 pound. At Session 4, she meets her weight loss goal (weight=249) and earns \$20. If she gains 2 pounds, for Session 5 (weight=251), she will not earn the \$20 incentive. Then, for Session 6, she would have to lose 3 pounds (weight=248) to earn the incentive because her weight loss goal of 1 pound is based on her lowest weight in the study so far which was 249. This is to ensure participants aren't reinforced for losing the same pound over and over again.

Families will also receive compensation for attendance. If families attend 6 out of 8 sessions or 8 out of 8 sessions, they will each receive \$25 and \$50, respectively.

Session 11 ~ 1 Hour; In Lab Session

Participants will have height/weight measured, do the thought training program, talk to staff about progress in the program, and receive money from the monetary incentives program. Participants will also complete surveys during this session.

PHASE 2: Sessions 12-19; Phone Sessions ~ 30 minutes Participants will talk to staff about progress in the program and do the thought training program.

During both phases of intervention, participants will be encouraged to send weekly weights from the provided scale. Participants will also be asked to log their activity related to the program in the MyFitnessPal app. Researchers will access the information and send feedback to the participants (via text, phone, and/or email) to help them succeed in the program.

Session 19 \sim 1 Hour; In Lab Session

Participants will have height/weight measured, do the thought training program, talk to staff about progress in the program, and complete surveys.

Session 20~ 1 Hour; In Lab Session

Participants will have height/weight measured and complete surveys. This session will take place after an 8 week no intervention follow up that follows Session 19.

If at any point during the study a child dips below the 85th percentile or the parent dips below a BMI of 25.0, the researcher will have a conversation with the family to inform them that they have moved from the overweight range to a healthy weight range. Participants will no longer have the 0.5 lb (child) or 1lb (parent) weight-loss goal. If participants change BMI categories during the monetary incentive portion of the study, the incentives will be contingent on weight-loss maintenance. Therefore, participants will receive the monetary incentive as long as they do not gain weight during that week. Some participants may wish to continue their weight-loss efforts to move further away from the overweight BMI category. The PI will check weights weekly to ensure participants are not losing too much weight.

The following surveys from the full protocol will be in hard copy form and will be stored in a locked cabinet in a locked office at the Center for Healthy Weight and Wellness:

Parent: Clinical interview, Eating Disorders Examination Questionnaire, Sociodemographic Questionnaire Child: Clinical interview, Kids Eating Disorders Survey

The following surveys from the full protocol will be collected via Qualtrics and will not contain any PHI: Parent: Consideration or Future Consequences Scale, Delay Discounting Task, Living to 75 Assessment, Palatable Eating Motives Scale

Child: Consideration or Future Consequences Scale, Delay Discounting Task, Living to 75 Assessment, Palatable Eating Motives Scale

Cohort 3 - Due to the COVID 19 outbreak, in-person assessments and interventions are no longer feasible. Therefore, the researchers will carry out these study components remotely. The programs that will be used are phone, Zoom, and Qualtrics.

WEEK 0 - Baseline Session: ~ 2 hours; In-Lab Group Session - All Baseline sessions were completed as planned in lab.

First, upon arriving to the lab, each dyad will be escorted to a private room and will complete the following: 1- Have height and weight measured.

2- Complete surveys: Consideration of Future Consequences Scale (CFCS), EDE-Q (Parent), KEDS (Child)

3- Complete the Delay Discounting Task, the Virtual Shopping Task, and Home Food Inventory. A letter was sent to each family explaining the change from in-home visits with the Cupboard inventory to the self-completed Home Food Inventory, due to growing concern over COVID-19.

4- Receive first assessment payment (\$40 dollars)

Following steps 1-4, the families will take part in a group session to learn the core components of the program in presentations by the research staff.

Weeks 1-14 \sim 2 hours; Weekly In-Lab Group Sessions - Due to the COVID 19 outbreak, in-person assessments and interventions are no longer feasible. Therefore, the researchers will carry out these study components remotely. The programs that will be used are phone, Zoom, and Qualtrics.

1. The day of their assigned parent group session, each family will email the study coordinator a photocopy of their food receipts, receipt forms, and food log. They will self-report weights via email as well. Payment will be completed via check request, Amazon Pay, or Forte.

2. Children will join a child-only Zoom group video session, and parents will join a parent-only Zoom video session. Each group will be led by a study team member. In these sessions, participants will do the thought training program, and talk to staff and other group members about progress in the program. Each parent-child dyad will meet via Zoom or phone at a separate time with a study team member to complete the case management portion of the program.

a. During the 15-week intervention, participants will be asked to log their activity related to the program in food logs. b. Researchers will access the information and send feedback to the participants (via text, phone, and/or email) to help them succeed in the program.

Throughout the baseline period, the study team will assess all participants' adherence levels through looking at data from the food logs and the collected receipts.

Once a family has been determined to be adhering to the study protocol, the participant will then be randomly assigned to either the 4-week, 7- week or 10-week baseline group. Participants who were assigned 4- week baseline, will now be eligible to start the intervention, those in the 7-week will complete three more weeks of baseline prior to the intervention.

An assessment session will take place the week the group starts the intervention, which will consist of

1- Self-reported weights via email

2- Complete surveys: EDE-Q (Parent), KEDS (Child) on Qualtrics

3- Complete EFT cue generation needed for thought training – See cohort 2 for description – this will be remotely done via Qualtrics.

4- Complete the Delay Discounting Task on Qualtrics and the Virtual Shopping Task via emailed instructions.

5- Review weekly receipts and receive receipt payment if applicable (\$25 dollars) via check request, Amazon Pay or Forte.

6- Receive assessment session payment (\$40 dollars) via check request, Amazon Pay or Forte.

7. Receive a EFT Cue Retrieval technology tutorial via emailed instructions, or a Zoom or phone session as requested – See cohort 2 for description.

Assessment measures must be completed the day of their assigned group sessions. Child and Parent Zoom-based group sessions will be conducted at their scheduled times, as well as scheduled case management.

Week 15 \sim Final Assessment - All assessment measures for week 15 will be conducted remotely, unless COVID-19 related restrictions are lifted, in which an in-lab visit for final measurements may be conducted.

1- Self-reported heights and weights

2- Complete surveys on Qualtrics: Consideration of Future Consequences Scale (CFCS), EDE-Q (Parent), KEDS (Child), Formative Questionnaire, TT Frequency of Use

3- Complete the Delay Discounting Task, Shelf Life Inventory, and Home Food Inventory on Qualtrics, and the Virtual Shopping Task via emailed instructions.

4- Review weekly receipts and receive payment if applicable (\$25 dollars) via check request, Amazon Pay or Forte.

5- Receive final assessment session payment (\$45 dollars) via check request, Amazon Pay or Forte.

Assessment measures must be completed the day of their assigned group sessions. Child and Parent Zoom-based group sessions will be conducted at their scheduled times, as well as scheduled case management.

Cohort 3 Compensation Breakdown

- Weekly Payment for Food Purchase Receipts (W1-W15) - \$25 per week = 375 total

- Baseline, Assessment 1 and Assessment 2 Payment = 125
- Total Payment per family = \$500 via check request, Amazon Pay or Forte.

All surveys and data will be collected remotely by study team members without PHI during sessions. All collected data will be securely stored in Box. All surveys will be done via Qualtrics.

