NOTIFICATION OF STUDY PROCEDURE CHANGE - Participants will receive a letter describing why the home-visits are cancelled and the Cupboard Inventory is replaced by the Home Food Inventory. Due to the immediate nature of this change, in order to protect the health of the participants, they will not be re-consented, rather they will just be notified of the change.

1.13 Provide a detailed description in sequential order of the study procedures following the consent process - DO NOT cut and paste from the Consent Document.

Describe study populations separately if they will be participating in different procedures

DESCRIBE:

- · Control populations, if applicable
- Any randomization, if applicable
- What participants will be asked to do/what happens in the study (in sequential order)
- · The time period over which procedures will occur
- Long-term follow-up and how it occurs

Cohort 1:

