Session 2- Baseline: ~ 1 Hour 30 Minutes:

During the baseline session, participants will complete the following:

1- Surveys: Consideration of Future Consequences Scale (CFCS), Palatable Eating Motives Scale (PEMS), and Living to 75 assessment.

2- Delay Discounting Task

- 3- Relative Reinforcing Value Task (will assess level of hunger before the task- hunger scale attached).
- 4- EFT or CONTROL cue generation needed for thought training.

EFT Cues: A brief cue will be generated in which participants talk about a specific future positive event where they imagine themselves in vivid detail. To generate the cues, participants in the EFT group will be given standardized instructions asking them to think about and list specific events that they are looking forward to in the future (ex: parties, holidays, etc.). Participants will be instructed to generate the EFT cue by describing their events, including a detailed description of themselves at the specific event. After the cue is created, participants will rate this cue for valence, salience, arousal, and the frequency and vividness of episodic associations. Participants who do not rate the cue at least 3 out of 5 for vividness will be asked to generate a new cue using a different event. After the participant has created their cues, they will save their cue for later use in the intervention.

Control Cues: To control for the timing and attention of the EFT cue, participants in the CONTROL group will generate cues that include a specific nutrition statements, selecting cues that they feel will be of personal benefit. To generate the cues, participants in the CONTROL group will select from a list of nutrition statements that they feel will be personally useful in making healthy decisions. After the cue is created, participants will rate this cue for salience. After the participant has created their cues, the participant will save their cue for later use in the intervention.

5- Technology Tutorial: Participants will be learning to use 3 major technologies for this study including:

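### Cohort 3 lists EFT cue generation before the Delay Discounting and Virtual Shopping tasks at the start of the intervention; if run in that order, the in-lab Week 0 value is the only one free of EFT

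*Combined protocol and SAP*

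**What the plan says.** Section 1.4 gives Cohort 3 a second aim and hypothesis, that EFT lowers Delay Discounting (DD). Section 1.13 asks the authors to "Provide a detailed description in sequential order of the study procedures following the consent process". Under it, Cohort 3 has DD and the Virtual Shopping Task at three points only:

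- **Week 0**, headed as the baseline session and done in the lab. The tasks come before the first group session.
- **The week a group starts the intervention.** Item 3 is "Complete EFT cue generation needed for thought training", item 4 is "Complete the Delay Discounting Task on Qualtrics and the Virtual Shopping Task via emailed instructions", and item 7 is "Receive a EFT Cue Retrieval technology tutorial via emailed instructions".
- **Week 15**, where "All assessment measures for week 15 will be conducted remotely, unless COVID-19 related restrictions are lifted".

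The only timing rule within a day is that "Assessment measures must be completed the day of their assigned group sessions". Cohort 3 refers to Cohort 2 for the content of cue generation. There it is an exercise in vividly imagining oneself at a future event, repeated with another event if the vividness rating is too low.

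The earlier cohorts use the other order. Cohort 1, Session 2 has DD as item 2 and "EFT or CONTROL cue generation needed for thought training" as item 4. Cohort 2, Session 3 has DD as item 3, then "Complete EFT or CONTROL cue generation needed for thought training" as item 4.

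The Cohort 3 analysis in sections 1.22 and 1.23 is graphical, plus the degree of change between baseline and treatment. It does not say to which phase the middle DD and shopping values belong. Section 1.23 justifies the sample by the amount of weekly data.

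**The concern.** A multiple-baseline design depends on observations taken just before the intervention starts, at staggered times. For DD and the Virtual Shopping Task only the middle assessment can supply such an observation. If cue generation comes first, the middle value already follows an EFT exercise, and the background in section 1.5 itself says that EFT reduces DD.

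Either coding of that value then causes trouble. Coded as treatment, its only comparator is the in-lab Week 0 value, so the EFT effect is mixed with the switch to remote testing, programme content and elapsed time. Coded as baseline, it may carry an acute cue effect into the reference value. With the coding unstated, the choice could be made after the data are seen. The weekly-data argument in section 1.23 does not help, because these two tasks are not done weekly.

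**Working it through.** The plan has no figure of its own to reproduce here; section 1.23 gives no power analysis.

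**Inputs.** Baseline lengths b = 4, 7 or 10 weeks, final assessment at Week 15, and n = 6 to 12 families (sections 1.3 and 1.13). As a check on the count, the assessment payments are 40 + 40 + 45 = 125, that is, three occasions.

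**Assumptions.** Baseline weeks count from Week 0; families are split equally over the three lengths; residuals are independent; Week 15 is remote. Standard errors (SE) are in residual SDs, for one role (parent or child) per family.

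**Notation.** e = EFT effect, m = lab-to-remote shift, s = drift per week. Within a family, d1 is the change from Week 0 to the middle value and d2 the change from the middle value to Week 15. Each has variance 2, with covariance -1.

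**Values before any EFT exercise, per participant.** Listed order: 1. Tasks first: 2.

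**Lab-to-remote shift, no drift**
- Listed order: d1 = e + m and d2 = 0. Only the sum e + m can be estimated, whatever b is, so staggering does not help.
- Tasks first: d1 = m and d2 = e. The estimate of e is the mean of d2, with SE = sqrt(2/n) = 0.58 (n = 6) and 0.41 (n = 12).

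**Linear drift and lab-to-remote shift**
- Listed order: d1 = e + m + b·s, so e is again not estimable.
- Tasks first: d1 = m + b·s and d2 = e + (15 - b)·s. With b centred at 7, the mean squared deviation is (9 + 0 + 9)/3 = 6 and the information on s is 6n × 2/3 = 4n. The mean of 15 - b is 8, so Var(e) = 2/n + 8²/(4n) = 18/n. SE = 1.73 (n = 6) and 1.22 (n = 12).

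**Linear drift only (m = 0): what the reorder costs**
- Listed order: Var(e) = [1.5 + 11²/(8²/2 + 4)]/n = (1.5 + 121/36)/n = 4.861/n. SE = 0.90 and 0.64.
- Tasks first: Var(e) = [1.5 + 11.5²/(7²/2 + 4)]/n = (1.5 + 132.25/28.5)/n = 6.140/n. SE = 1.01 and 0.72.

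**A free effect for each week.** Not estimable in either order. As listed, EFT coincides with every week after 0; with tasks first, it coincides with Week 15.

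**What stays in the reordered change.** 15 - b = 11, 8 or 5 weeks (mean 8) of drift and programme content.

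**Listed order, middle value coded as baseline.** If the acute cue effect is a fraction f of the Week 15 effect, the change to Week 15 shows 1 - f of the effect. The documents do not give f. At f = 0 nothing is lost and at f = 1 everything is. If an acute effect fades by Week 15, f exceeds 1 and the sign reverses, so 0 to 100% is not a bound.

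**The case against.** - **The list need not be the running order.** This stands. Staff could run the tasks first without breaching any rule, so the point is conditional. The request for sequential order and the opposite order in Cohorts 1 and 2 make the condition worth settling. If order is free, it may also differ between families.
- **The middle value does have a natural phase.** This largely stands. Only Week 0 is headed as baseline, the middle session is dated to the week the intervention starts, and the payment list separates Baseline from Assessments 1 and 2. The likelier reading is a first intervention-phase value. Section 1.22 does not say so, however, and that reading leaves Week 0 as the sole comparator.
- **Thought training may already run in the baseline weeks.** Section 1.13 describes it for the Weeks 1-14 sessions without limiting it to the intervention phase. Read literally, the middle value would follow thought training in either order. This stands as a precondition for the reorder.
- **It may be too late.** Section 1.12 says that enrollment is complete. In section 1.15 the Home Food Inventory, used at Week 0, was attached on 03/12/20 and the Shelf Life Survey, used at Week 15, on 06/15/20. That is 95 days, or 13.6 weeks. If Week 0 fell by about mid-March (an inference, since no session dates are given), even the 10-week group had passed its phase change by the later date.
- **The reorder does not buy precision.** Under a drift-only model it loses some. The gain is that e can be separated from m at all.

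**Conclusion.** The point holds in a limited form, and its severity is minor to moderate. If the list is followed and Week 15 is remote, Week 0 is the only pre-EFT value for DD and the Virtual Shopping Task. An EFT effect on them then cannot be separated from the lab-to-remote shift at any sample size. If Week 15 returns to the lab, Week 0 and Week 15 share a setting and the shift cancels between them, but 15 weeks of drift and programme content remain.

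Three stronger readings go beyond the documents:

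- A reader might infer that the protocol requires cue generation first. It requires only the same day.
- A reader might infer that the Cohort 3 shopping aim fails too. Food receipts are collected weekly and are unaffected; the damage is to Aim 2 and one Aim 1 task.
- A reader might infer that DD is shown to be biased. The size of any acute cue effect is not given, and the bias from that source could be nil.

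Nor would the reorder create full multiple-baseline control: each task would still have three points, with no control group.

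**What to change.** 1. **Sessions still to come.** Place both tasks before cue generation and define that value as the last pre-EFT point. First reconcile the Weeks 1-14 thought-training sentence with an EFT-free baseline, since otherwise the reorder achieves nothing. Then report the change from phase change to Week 15 for Aim 2, stating that 5 to 11 weeks of drift and programme content remain in it. If Week 15 is done in the lab, say that this change contains the remote-to-lab shift. The cost is a reorder of same-day remote items with no added burden, and the precision loss under a drift-only model shown above.
2. **Sessions already run**, which may be most or all of them. Record the order actually used. Where cues came first, treat the middle value as post-cue and report Aim 2 as an uncontrolled pre-post comparison that includes the lab-to-remote shift. This is labelling and reporting only.
3. **Section 1.22.** State the phase of the middle DD and Virtual Shopping values.
4. **Section 1.23.** Limit the weekly-data rationale to receipts, food logs and weights.

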Family-based treatments (FBT) for obesity have been shown to be effective in achieving significant weight reduction in overweight or obese children and parents [Altman & Wilfley, 2015]. One component of the current FBT program used in this study that has received little attention is thought training, specifically episodic future thinking (EFT). EFT teaches individuals to pre-experience events, or think prospectively, about future events as if they were happening now and has been shown to reduce delay discounting (DD) which is defined as discounting smaller rewards now for a larger reward in the [Daniel, Said, Stanton, & Epstein]. Furthermore, EFT has been shown to help people purchase fewer calories when they are grocery shopping [Hollis-Hansen et al., 2019], thereby displaying potential to be an effective measure in modulating the food environment in homes and may play a role in changing eating behaviors related to weight loss [Appelhaus et al., 2019].

Given the power of EFT in promoting the purchase of fewer calories, it is plausible that EFT training focused around grocery shopping during FBT could help shift one's thought processes towards healthier food choices, promoting behavioral change that has lasting impact on the home environment. Thus, the primary purpose of this study is to assess whether EFT training promotes active behavioral change pertaining to grocery shopping during FBT. In turn, this resulting behavior change could lead to healthier eating behavior and may promote weight loss for the whole family.

1.6 Literature cited/references (if attaching a grant enter N/A):

Leahey et al. (2016). A randomized controlled trial testing an internet delivered cost-benefit approach to weight loss mantenance. Preventative Medicine, 92, 51-57.

John et al. (2010). Financial incentives for extended weight loss: a randomized, controlled trial. Journal of General Internal Medicine, 26, 621-626.

Volpp et al. (2008). A randomized controlled trial of financial incentives for weight loss. JAMA, 22, 2631-2637.

Ries. (2012). Financial incentives for weight loss and healthy behaviors. Healthcare Policy, 7, 23-28.

Atance, & O'Neill. (2001). Episodic future thinking. Trends in Cognitive Sciences, 5, 533-539.

Daniel et al. (2013). The future is now: Comparing the effect of episodic future thinking on impulsivity in lean and

obese individuals. Appetite, 71, 120-125.

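### Cohort 3 omits the Home Food Inventory from the assessment at EFT start, so its Week 0 to Week 15 change cannot be divided into pre-EFT and EFT phases

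*Combined protocol and SAP*

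**What the plan says.** Section 1.13, Cohort 3, sets out three assessments.

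- **Week 0.** Families "Complete the Delay Discounting Task, the Virtual Shopping Task, and Home Food Inventory". The plan reports that "All Baseline sessions were completed as planned in lab". The same item describes "the change from in-home visits with the Cupboard inventory to the self-completed Home Food Inventory", which was made because of COVID-19. A group session teaching the program's core components follows directly.
- **EFT start.** "An assessment session will take place the week the group starts the intervention, which will consist of" a list of seven items. The tasks on it are given as "Complete the Delay Discounting Task on Qualtrics and the Virtual Shopping Task via emailed instructions". The other items are self-reported weight, eating-disorder surveys, cue generation, receipts, payment and a cue tutorial. Neither inventory is listed.
- **Week 15.** Both inventories are listed, online: "Complete the Delay Discounting Task, Shelf Life Inventory, and Home Food Inventory on Qualtrics". Completion is remote "unless COVID-19 related restrictions are lifted, in which an in-lab visit for final measurements may be conducted".

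The weekly sessions between these collect receipts, receipt forms, food logs and weights. Section 1.7 states that every Cohort 3 family receives EFT and that only its starting time differs. Section 1.22 plans a graphical analysis and an assessment of change from baseline to treatment over three replications. Section 1.5 gives the reason for interest in the home: EFT training might work by "promoting behavioral change that has lasting impact on the home environment".

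**The concern.** A multiple-baseline design draws its inference from what happens to a measure when the phase changes, and from whether that happens at the staggered times. A measure taken only at the two ends has no value at the phase change. Any Week 0 to Week 15 movement in the Home Food Inventory could come from the weeks before EFT, from the program teaching that begins at Week 0, from pandemic changes in what households stock, or from EFT. Nothing in section 1.22 warns against crediting the whole change to EFT, and the rationale in section 1.5 invites that reading.

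**Working it through.** The plan gives no sample-size or power figure for Cohort 3, so there is none to reproduce. The check is a count of the schedule, followed by timeline arithmetic.

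**1. When each measure is taken (section 1.13, Cohort 3)**

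| Measure | Week 0 | Weekly sessions | EFT start | Week 15 |
|---|---|---|---|---|
| Delay Discounting Task | yes | no | yes | yes |
| Virtual Shopping Task | yes | no | yes | yes |
| Food receipts | no | yes | yes | yes |
| Home Food Inventory | yes | no | **no** | yes |
| Shelf Life Inventory | no | no | **no** | yes |

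The two tasks have three values each, one of them at the phase boundary. The Home Food Inventory has two values and the Shelf Life Inventory one, with none at the boundary.

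**2. What the Week 0-15 interval contains**

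This assumes that baselines last exactly 4, 7 or 10 weeks and that EFT runs to Week 15. EFT weeks = 15 − baseline weeks.

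| Baseline group | Pre-EFT share | EFT weeks by Week 15 |
|---|---|---|
| 4 weeks | 4/15 = 27% | 15 − 4 = 11 |
| 7 weeks | 7/15 = 47% | 15 − 7 = 8 |
| 10 weeks | 10/15 = 67% | 15 − 10 = 5 |

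Section 1.3 gives the intervention as 4-8 weeks. The 11 weeks left after a 4-week baseline fall outside that range, and section 1.13 also refers to the whole period as a 15-week intervention. These statements must be reconciled. If at most 8 weeks applies, at least 15 − 8 = 7 of the 15 weeks (47%) lie outside the intervention in every group.

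**3. Can the randomised onset groups supply the contrast instead?**

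The groups differ in EFT duration (11, 8 and 5 weeks), so a linear trend in the inventory across groups could be tested. No effect size or alpha is given, so I assume two-sided alpha 0.05 and equal groups of n families.

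- Mean duration is 8 weeks, so the sum of squares is n × (3² + 0² + 3²) = 18n.
- Let d be the difference between the 4-week and 10-week groups in SD units. The slope is d/6 per week.
- Noncentrality = (d/6) × √(18n) = d × √(n/2), with 3n − 2 degrees of freedom. Power counts rejection in the direction of the effect.

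| Families | n per group | d needed for 80% power | Power at d = 0.8 |
|---|---|---|---|
| 6 | 2 | 3.76 | 9.1% |
| 9 | 3 | 2.67 | 13.4% |
| 12 | 4 | 2.20 | 17.5% |

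This contrast is valid in principle because onset is randomised. It has no EFT-free group, however, and would detect only differences of more than two SDs with reasonable probability.

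**The case against.** The strongest reply is that no stated objective depends on the inventories. Section 1.4 gives the Cohort 3 aims as grocery shopping behavior and delay discounting, and the measures for both are collected at EFT start. Section 1.5 offers the home environment only as a plausible downstream effect, and section 1.22 plans no inventory analysis. This stands, and it limits the point to supporting evidence. A reader might infer that the gap undermines Cohort 3's aims; the documents do not support that.

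Four further replies have force.

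- **Absolute wording.** A reader might infer that the inventory carries no information at all about EFT. Randomised onset leaves the between-group contrast in step 3 of the working, which is very weak but not nil.
- **Shelf Life Inventory.** It is tempting to treat this as a second measure of the home food environment. The documents never describe its content; section 1.15 lists only a file name. What can be said is that one time point yields no change.
- **Setting.** A reader might infer that moving from lab to remote completion biases the change. Week 0 lists the inventory among in-lab items but also calls it self-completed, and Week 15 could be in the lab. Where families filled it in at either time is not settled.
- **Timing.** Section 1.12 says recruitment was complete as of 2/3. The Home Food Inventory form was attached on 03/12/20 and the Shelf Life form on 06/15/20. Session dates are not given, but some or all EFT-start assessments may have passed, and the Shelf Life form may postdate them.

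It is also fair to say that one added value does not remove pandemic effects or separate EFT from the family-based treatment given with it. It does give a pre-EFT change to set against the EFT-phase change, and the stagger places the boundary at different program weeks.

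**Conclusion.** The point holds as a limit on supporting evidence. The Home Food Inventory has no value at EFT start, so the within-family baseline-to-treatment comparison that the plan relies on cannot be made for it. Its Week 0-15 change contains 27%, 47% or 67% pre-EFT time, and comparing onset groups needs a difference of roughly 2.2 to 3.8 SD for 80% power.

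The percentages describe the composition of the interval; they do not measure bias. They assume exact baseline lengths and EFT to Week 15. Section 1.13 makes assignment depend on demonstrated adherence, so actual lengths may differ. The power figures rest on the assumed alpha and equal groups. The missing boundary value itself rests on none of these assumptions.

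**What to change.** 1. Add the Home Food Inventory, in the Qualtrics form already used at Week 15, to the assessment at which each group begins EFT, completed before cue generation.
2. Keep Week 0 in the analysis. Compare change from Week 0 to EFT start (pre-EFT) with change from EFT start to Week 15 (EFT phase), each divided by its number of weeks, and show this for the three staggered groups side by side. Treating Week 0 as merely descriptive would discard the only pre-EFT change that the added value creates.
3. Where the EFT-start assessment has already passed, state that the Week 0-15 inventory change is descriptive and supports no conclusion about EFT.
4. Report the Shelf Life Inventory as a Week 15 description only, unless it can still be given at EFT start. Say what it measures.
5. Reconcile the intervention length in section 1.3 with the schedule in section 1.13.

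The cost is some extra minutes per family at one remote assessment that is already scheduled and already paid ($40), with no added visit. For groups past that point, the cost is a sentence in the analysis section.
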